Attachment 5: Inhibitors and Inducers of CYP3A

The table below shows the classification of commonly used inhibitors and inducers of CYP3A enzymes. Further information can be found at the following websites:

<https://www.fda.gov/drugs/drug-interactions-labeling/drug-development-and-drug-interactions-table-substrates-inhibitors-and-inducers>¹¹

<http://medicine.iupui.edu/clinpharm/ddis/main-table/>.¹⁰

Inhibitors of CYP3A	Inducers of CYP3A
Strong inhibitors:	
Boceprevir	carbamazepine
Clarithromycin	barbiturates
Cobicistat	efavirenz
Indinavir	glucocorticoids
Itraconazole	modafinil
Ketoconazole	nevirapine
Mibepradil	oxcarbazepine
Nefazodone	phenobarbital
Nelfinavir	phenytoin
posaconazole ^a	pioglitazone
Ritonavir	rifabutin
Saquinavir	rifampin
Suboxone	St. John's Wort
Telaprevir	troglitazone
Telithromycin	
Troleandomycin	
Moderate inhibitors:	
Amiodarone	
Amprenavir	
Aprepitant	
Atazanavir	
Ciprofloxacin	
Crizotinib	
Darunavir	
diltiazem	
Dronedarone	
Erythromycin	
Fluconazole	
Fosamprenavir	
grapefruit juice	
Seville orange juice	
Verapamil	
voriconazole ^a	
Amiodarone	
Weak inhibitors:	
Cimetidine	
Fluvoxamine	
All other inhibitors:	
Chloramphenicol	
Delavirdine	
diethyl-dithiocarbamate	
Gestodene	
Mifepristone	
Norfloxacin	
Norfluoxetine	
star fruit	

^a Classification based on internal data.

Attachment 6: Intrathecal Drug Doses by Age

Age (years)	Intrathecal Drug Doses (mg)			
	Methotrexate	Hydrocortisone*	Prednisolone*	Cytarabine
<1	8	8	4	15
≥1 to <2	10	10	6	20
≥2 to <3	12	12	8	25
≥3	15	15	10	30

*Other corticosteroids may be administered as per local supply provided that the steroid equivalent dose is equal to the prednisolone dose above.

Attachment 7: Blood Volume Tables**Estimated Maximum Volume of Blood to be Collected From all Subjects in Part 1, by Study Phase and Treatment Cycle**

Type of Sample ^{a,b}	Volume per Sample	No. of Samples per Subject	Approximate Total Volume of Blood ^c
Screening			
Safety			
Hematology	2.5 – 5.0 mL	1	2.5 – 5.0 mL
Serum chemistry	2.5 – 5.0 mL	1	2.5 – 5.0 mL
Serum β-hCG pregnancy tests ^d	2.5 mL	1	2.5 mL
HIV, Hepatitis B, C serologies	2.5 – 5.0 mL	1	2.5 – 5.0 mL
Tetanus, pneumococcal titers	2.5 – 5.0 mL	1	2.5 – 5.0 mL
Cycle 1			
Safety			
Hematology	2.5 – 5.0 mL	4	10.0 – 20.0 mL
Serum chemistry	2.5 – 5.0 mL	4	10.0 – 20.0 mL
Serum β-hCG pregnancy tests ^d	2.5 mL	1	2.5 mL
Pharmacokinetic samples	0.6 mL	10	6.0 mL
Pharmacodynamic samples	4.0 – 6.0 mL	4	16.0 – 24.0 mL
Biomarker samples	1.2 mL	2	2.4 mL
Protein binding	1.0 mL	1	1.0 mL
Cycle 2			
Safety			
Hematology	2.5 – 5.0 mL	2	5.0 – 10.0 mL
Serum chemistry	2.5 – 5.0 mL	2	5.0 – 10.0 mL
Serum β-hCG pregnancy tests ^d	2.5 mL	1	2.5 mL
Pharmacokinetic samples	0.6 mL	5 ^e	3.0 mL
Pharmacodynamic samples	4.0 – 6.0 mL	1 ^e	4.0 – 6.0 mL
Biomarker samples	1.2 mL	1 ^e	1.2 mL
Cycle 3			
Safety			
Hematology	2.5 – 5.0 mL	2	5.0 – 10.0 mL
Serum chemistry	2.5 – 5.0 mL	2	5.0 – 10.0 mL
Serum β-hCG pregnancy tests ^d	2.5 mL	1	2.5 mL
End-of-Treatment Visit			
Safety			
Hematology	2.5 – 5.0 mL	1	2.5 – 5.0 mL
Serum chemistry	2.5 – 5.0 mL	1	2.5 – 5.0 mL
Pharmacodynamic samples	4.0 – 6.0 mL	1	4.0 – 6.0 mL
Biomarker samples	1.2 mL	1	1.2 mL
First Follow-up Assessment			
Safety			
Tetanus, pneumococcal titers ^f	2.5 – 5.0 mL	1	2.5 – 5.0 mL
Monotherapy Cycle 1-3 (if applicable)			
Safety			
Hematology	2.5 – 5.0 mL	3	7.5 – 15.0 mL
Serum chemistry	2.5 – 5.0 mL	3	7.5 – 15.0 mL
Serum β-hCG pregnancy tests ^d	2.5 mL	3	7.5 mL
End-of-Monotherapy Visit (if applicable)			
Safety			
Hematology	2.5 – 5.0 mL	1	2.5 – 5.0 mL
Serum chemistry	2.5 – 5.0 mL	1	2.5 – 5.0 mL
Pharmacodynamic samples	4.0 – 6.0 mL	1	4.0 – 6.0 mL
Biomarker samples	1.2 mL	1	1.2 mL
Approximate Total^g			139.0 - 230.5 mL

β-hCG=beta-human chorionic gonadotropin; HIV=human immunodeficiency virus.

- a. Repeat or unscheduled samples may be taken for safety reasons or technical issues with the samples.
- b. Sample volumes will be adjusted according to standards for pediatric subjects.
- c. Calculated as number of samples multiplied by amount of blood per sample.
- d. Serum pregnancy test to be performed only if urine is unavailable.
- e. These samples may be collected in Cycle 2 or Cycle 3, but not both.
- f. Subjects who enter monotherapy will have sample taken at End-of-Monotherapy Visit
- g. An additional biomarker sample may be taken if PD occurs during a follow-up visit

Note: An indwelling intravenous cannula may be used for blood sample collection.

Estimated Maximum Volume of Blood to be Collected From Each Subject in Part 2, by Study Phase and Treatment Cycle

Type of Sample ^{a,b}	Volume per Sample	No. of Samples per Subject	Approximate Total Volume of Blood ^c
Screening			
Safety			
Hematology	2.5 – 5.0 mL	1	2.5 – 5.0 mL
Serum chemistry	2.5 – 5.0 mL	1	2.5 – 5.0 mL
Serum β-hCG pregnancy tests ^d	2.5 mL	1	2.5 mL
HIV, Hepatitis B, C serologies	2.5 – 5.0 mL	1	2.5 – 5.0 mL
Tetanus, pneumococcal titers	2.5 – 5.0 mL	1	2.5 – 5.0 mL
Cycle 1			
Safety			
Hematology	2.5 – 5.0 mL	4	10.0 – 20.0 mL
Serum chemistry	2.5 – 5.0 mL	4	10.0 – 20.0 mL
Serum β-hCG pregnancy tests ^d	2.5 mL	1	2.5 mL
Pharmacokinetic samples	0.6 mL	4 ^e	2.4 mL
Pharmacodynamic samples	4.0 – 6.0 mL	4	16.0 – 24.0 mL
Biomarker samples	1.2 mL	2	2.4 mL
Cycle 2			
Safety			
Hematology	2.5 – 5.0 mL	2	5.0 – 10.0 mL
Serum chemistry	2.5 – 5.0 mL	2	5.0 – 10.0 mL
Serum β-hCG pregnancy tests ^d	2.5 mL	1	2.5 mL
Cycle 3			
Safety			
Hematology	2.5 – 5.0 mL	2	5.0 – 10.0 mL
Serum chemistry	2.5 – 5.0 mL	2	5.0 – 10.0 mL
Serum β-hCG pregnancy tests ^d	2.5 mL	1	2.5 mL
Pharmacodynamic samples	4.0 – 6.0 mL	1 ^f	4.0 – 6.0 mL
Biomarker samples	1.2 mL	1 ^f	1.2 mL
End-of-Treatment Visit			
Safety			
Hematology	2.5 – 5.0 mL	1	2.5 – 5.0 mL
Serum chemistry	2.5 – 5.0 mL	1	2.5 – 5.0 mL
Pharmacodynamic samples	4.0 – 6.0 mL	1	4.0 – 6.0 mL
Biomarker samples	1.2 mL	1	1.2 mL
First Follow-up Assessment			
Safety			
Tetanus, pneumococcal titers ^g	2.5 – 5.0 mL	1	2.5 – 5.0 mL
Monotherapy Cycle 1-3 (if applicable)			
Safety			
Hematology	2.5 – 5.0 mL	3	7.5 – 15.0 mL
Serum chemistry	2.5 – 5.0 mL	3	7.5 – 15.0 mL
Serum β-hCG pregnancy tests ^d	2.5 mL	3	7.5 mL
End-of-Monotherapy Visit (if applicable)			
Safety			
Hematology	2.5 – 5.0 mL	1	2.5 – 5.0 mL
Serum chemistry	2.5 – 5.0 mL	1	2.5 – 5.0 mL

MUGA	multiple-gated acquisition scan
NCI	National Cancer Institute
NHL	non-Hodgkin lymphoma
ORR	overall response rate
PBPK	physiologically-based pharmacokinetic
PD	progressive disease
PET	positron emission tomography
P-gp	P-glycoprotein
PQC	Product Quality Complaint
PR	partial response
RICE	rituximab, ifosfamide, carboplatin, etoposide, and dexamethasone
RVICI	rituximab, vincristine, ifosfamide, carboplatin, idarubicin, and dexamethasone
SET	Study Evaluation Team

SF	shortening fraction
SJS	Stevens-Johnson Syndrome
SLL	small lymphocytic lymphoma
SUSAR	suspected unexpected serious adverse reaction
ULN	upper limit of normal
Vd/F	apparent (oral) volume of distribution

1. INTRODUCTION

This clinical study is a part of a comprehensive ibrutinib clinical development plan to evaluate the safety and efficacy of ibrutinib for subjects with B-cell malignancies. This is a 2-part, multicenter study. A safety and pharmacokinetic run-in part (Part 1) will be conducted before starting the randomized part (Part 2) of the study. Part 2 is a randomized, open-label, Phase 3 study to compare the safety and efficacy of ibrutinib in combination with chemoimmunotherapy (CIT [RICE or RVICI]) versus CIT alone in children and young adult subjects with relapsed or refractory mature B-cell non-Hodgkin's lymphoma (NHL).

The purpose of the statistical analysis plan (SAP) is to lay out key elements including definition and statistical methods for the planned analyses for the primary, secondary and safety endpoints.

1.1. Trial Objectives

Primary Objective

- Run-in Part (Part 1): Confirm that the pharmacokinetics in pediatric subjects is consistent with that in adults.
- Randomized Part (Part 2): Assess efficacy (event-free survival [EFS]) of ibrutinib in combination with RICE or RVICI background therapy compared to RICE or RVICI background therapy alone.

Secondary Objectives

The secondary objectives for Run-in Part (Part 1) are:

- Evaluate the safety and tolerability of ibrutinib in combination with RICE or RVICI background therapy in pediatric subjects with B-cell malignancies
- Assess anti-tumor activity of ibrutinib as add-on to RICE or RVICI regimens
- Assess disease-specific biomarkers
- Assess the pharmacodynamic response
- Acceptability and palatability assessment of all ibrutinib formulations

The secondary objectives for Randomized Part (Part 2) are:

- Evaluate the safety and tolerability of ibrutinib in combination with RICE or RVICI background therapy in pediatric subjects and young adults with B-cell malignancies
- Determine the overall response rate (ORR)
- Evaluate tumor volume reduction at Day 14
- Determine the number and proportion of subjects who proceed to stem cell transplantation
- Evaluate the time to response

- Measure the duration of response
- Evaluate long-term survival (EFS at 2 and 3 years)
- Evaluate overall survival
- Assess disease-specific biomarkers
- Assess the pharmacodynamic response, if deemed appropriate based on Part 1 results
- Assess the population pharmacokinetics of ibrutinib in pediatric subjects and young adults
- Acceptability and palatability assessment of all ibrutinib formulations

1.2. Trial Design

This is a 2-part, multicenter study. A safety and pharmacokinetic run-in part (Part 1) will be conducted before starting the randomized part (Part 2) of the study. Part 2 is a randomized, open-label, Phase 3 study to compare the safety and efficacy of ibrutinib in combination with CIT (RICE or RVICI) versus CIT alone in children and young adult subjects with relapsed or refractory mature B-cell NHL. All subjects in Part 1 will receive ibrutinib in combination with CIT (investigator choice of RICE or RVICI); 6 to approximately 24 pediatric subjects (1 to <18 years) will be enrolled to allow confirmation of the dose regimen. Enrollment will begin with children in the 2 older age groups (6-11, 12-17 years) to assess pharmacokinetic and safety data before allowing enrollment of children in the youngest age group (1-5 years). The SET will meet to decide on any changes to the starting dose for each age group, and when enrollment may begin for the youngest age group. At a minimum, the first 2 subjects in each age group will enroll into Part 1 before recruitment of children in that age group will begin in Part 2. In Part 2, approximately 72 additional subjects will be randomized in a 2:1 ratio to receive ibrutinib in combination with CIT (investigator choice of RICE or RVICI) or CIT alone; at least 40 subjects are targeted to be of age 1 to <18 years and at least 10 of the 40 subjects are targeted to be age <11 years. Subjects will be stratified by histology (Burkitt lymphoma [BL]/Burkitt leukemia [B-AL] versus other) and by background therapy (RICE versus RVICI). Pharmacokinetic samples will be obtained during Part 2 of the study to characterize the pharmacokinetics in pediatric subjects.

Part 1 and Part 2 of the study will be conducted in 3 phases: a Pretreatment (Screening) Phase, a Treatment Phase, and a Posttreatment Phase. The Treatment Phase will extend from enrollment/randomization until 1 of the following: 1) completion of 3 cycles of therapy, 2) transplantation, if clinically indicated, or 3) disease progression, whichever comes first. Subjects will begin the Posttreatment Phase after completion of combination therapy. During the Posttreatment Phase, subjects on ibrutinib with a response of PR or better will continue on ibrutinib monotherapy for three 28-day cycles as described below (see Dosage and Administration). All subjects will be followed to assess disease progression as described below (see Efficacy Evaluations/Endpoints). The Posttreatment Phase will continue until death, loss to follow up, consent withdrawal, or study end, whichever occurs first. The end of study is defined as when approximately 60 EFS events have occurred in Part 2 (death, disease progression, or

lack of CR or PR after 3 cycles of treatment based on blinded independent event review), or the sponsor terminates the study, whichever comes first.

1.3. Statistical Hypotheses for Trial Objectives

The primary statistical hypothesis of this study is that the addition of ibrutinib to a salvage CIT regimen will extend EFS compared to CIT alone in pediatric and young adult subjects with relapsed or refractory mature B-cell NHL.

For the primary efficacy analysis, EFS will be compared between treatment groups using a non-stratified log-rank test. The estimate of the hazard ratio between the 2 treatment groups and its associated 90% confidence interval will be computed based on the non-stratified Cox proportional hazards model.

1.4. Sample Size Justification

Since Part 1 is to confirm that the pharmacokinetics in pediatric subjects is consistent with adults, no formal power calculations to pre-determine sample size were performed. The required number of subjects in Part 1 is based on pharmacokinetics results and clinical judgment.

In Part 2, approximately 72 subjects will be randomized. The sample size calculation for the randomized part (Part 2) is based on the assumption of 100% improvement (hazard ratio = 0.5) in median EFS in subjects receiving ibrutinib plus CIT (RICE or RVICI) compared with CIT (RICE or RVICI) (10 months versus 5 months). Utilizing a 2:1 randomization, this study will enroll approximately 72 subjects (approximately 48 subjects treated with ibrutinib [and RICE or RVICI background therapy]) during Part 2. Based on a total of 60 events for the 2 treatment groups, this study will have at least 80% power, given a 1-sided alpha of 0.05. An accrual rate of 1.44 subjects per month will result in a study duration of approximately 4.2 years.

1.5. Randomization and Blinding

Central randomization will be implemented in Part 2 of this study. Subjects will be randomly assigned to 1 of 2 treatment groups based on a computer-generated randomization schedule prepared before the study by or under the supervision of the sponsor. The randomization will be balanced by using randomly permuted blocks and will be stratified by histology and background therapy, then randomized in a 2:1 ratio to either Treatment Arm A (ibrutinib and RICE or RVICI background therapy) or Treatment Arm B (RICE or RVICI background therapy only). The interactive web response system (IWRS) will assign a unique treatment code, which will dictate the treatment assignment and matching study drug kit for the subject. The requestor must use his or her own user identification and personal identification number when contacting the IWRS, and will then provide the relevant subject details to uniquely identify the subject.

As this is an open-label study, blinding procedures are not applicable.

2. GENERAL ANALYSIS DEFINITIONS

Part 1 and Part 2 will be analyzed separately. The below specifications apply mainly to Part 2 unless otherwise noted.

2.1. Visit Windows

Visit windowing will be based on phases and cycles:

Pretreatment (Screening) Phase: The Screening Phase will occur within 14 days before administration of study drug.

Treatment Phase: The Treatment Phase will extend from enrollment/randomization until 1 of the following: 1) completion of 3 cycles of therapy, 2) transplantation, if clinically indicated, or 3) disease progression, whichever comes first.

Posttreatment Phase: Subjects will begin the Posttreatment Phase after completion of combination therapy. This is defined as starting from the last dose of study medication + 1 day until death, loss to follow up, consent withdrawal, or study end, whichever occurs first.

2.2. Pooling Algorithm for Analysis Centers

The data from all investigative centers (study sites) will be pooled for all analyses.

2.3. Analysis Sets

2.3.1. Efficacy Analysis Set

The intent-to-treat (ITT) Population will consist of all randomized subjects; subjects will be analyzed based on randomization, regardless of study drug received. The ITT population will be used for all efficacy analyses, subject disposition and biomarker analyses. The primary efficacy analysis is based on the ITT population for data collected in the Part 2. For Part 1, efficacy will be provided as a secondary endpoint.

2.3.2. Safety Analysis Set

The Safety population will consist of all subjects who received at least 1 dose of treatment. The safety population will be used for all safety analyses and subjects will be analyzed based on actual study drug received.

2.4. Definition of Subgroups

Subgroup analysis will be performed for the selected variables to assess the internal consistency of the treatment benefit and/or safety (Table 1). The subgroup variables and the cutoff values are subject to change if warranted to better represent the data.

Table 1: Subgroup Definitions

Subgroup	Definition of Subgroup	Analysis Type
Age	1-5 years, 6-11 years, 12-17 years	D, E, S
Sex	Male, Female	D, E, S
Race	White, Non-White	D, E, S
Histology/Diagnosis	Burkitt lymphoma [BL]/Burkitt leukemia [B-AL] versus DLBCL vs. other	E
Background therapy	RICE versus RVICI	E
Geographic region	United States, Europe including Eastern Europe, and Other	D, E, S
Elevated LDH at Baseline	No (<350 U/L), Yes (≥ 350 U/L)	E
Phosphor-BTK, as well as SYK, STAT3, caspase-3, BCL-xL, and cIAP1 expression	B-cell Proteomics	E
B-cell receptor (BCR)/CD79B, CARD11, and MYD mutations	BCR pathway mutations	E
c-MYC, immunoglobulin, and T-cell receptor gene rearrangements at baseline	Baseline genetics	E
Concomitant use of any CYP3A inhibitor	Yes, No	S

Insert table abbreviations

Cytopenia is defined as yes if platelet count $\leq 100,000/\mu\text{L}$, Hgb $\leq 11\text{ g/dL}$, or ANC $\leq 1500/\mu\text{L}$ is observed.

analysis type D= demographic and baseline disease characteristics

analysis type E= efficacy (EFS, OS, ORR)

analysis type S= safety (adverse events)

2.5. Study Day and Cycle Day

Assessments will be presented chronologically by study day or cycle day as described below.

For efficacy data, the randomization date is considered as the reference date (Day 1). For safety data, date of first dose of study medication (randomization date for subjects who have been randomized but not treated) will be used as the reference date (Day 1).

Reference date (Day 1) = randomization date (for efficacy data), or first dose date of study medication (for safety data).

Study Day = assessment date – reference date + 1 for assessment performed on or after the reference date; assessment date – reference date for assessment performed before the reference date.

Cycle Day = assessment date - date of the first dose for the cycle + 1.

Cycles

In defining treatment cycles in a combination therapy setting, the entire combination must be taken into account. Therefore, the nominal cycles as defined in protocol and recorded on the Case Report Form (CRF) will be used in the statistical analyses.

Cycles will be 28 days long; however, if count recovery occurs quickly and the investigator deems a subject ready to proceed with the next cycle of therapy, cycles can be shortened to as few as 21 days. As long as there is no disease progression after Cycle 1 or 2, a second and third cycle of therapy will be given, respectively.

2.6. Baseline and Endpoint

Unless specified otherwise, the baseline value is defined as the last non-missing value collected on or before the administration of the first dose of study medication. For subjects who have been randomized but not treated with any dose, randomization date will be used as the reference date for baseline value calculation.

2.7. Imputation Rules for Missing AE Date/Time of Onset/Resolution

In general, imputation of missing dates will be made for AE onset date, AE resolution date, date of death, start and end dates of prior, concomitant and subsequent therapies, and date of initial diagnosis according to the following rules. Start date will be imputed before end date.

- If date is completely missing, no imputation will be made.
- If year is missing, no imputation will be made.
- If only year is present but month and day are missing, then June 30th will be used.
- If only day is missing but year and month are available, then the 15th of the month will be used.

However, the above imputations will be modified by the following rules:

- For initial diagnosis if such imputed date is on or after the randomization date, then randomization date - 1 will be used.
- If such imputed date for prior therapies or initial diagnosis is on or after the randomization date, then randomization date - 1 will be used. If such imputed date for subsequent therapies is before date of last dose, then date of last dose +1 will be used.
- The imputed start date for subsequent therapies will be adjusted sequentially using the following steps:
 - If the imputed start date is before the treatment discontinuation date or last dose date if no treatment discontinuation date but in the same year and month, then the treatment discontinuation date or last dose date if no treatment discontinuation date will be used.
 - If subsequent therapy end date is not missing and is before the imputed subsequent therapy start date, then the subsequent therapy end date will be used as the start date.
- If the imputed date is for a date of death and is before the last date that the subject is known to be alive, the latter date will be used.
- The imputed AE start date will be adjusted sequentially using the following steps:
 - If the imputed date is in the same year and month as but day before the first dose date, then the first dose date will be used, or if it is in the same year and month as but day after the last dose date + 30 days, then the last dose date + 30 days will be used.

- If AE end date is not missing and the imputed AE start date is after the AE end date, then the AE end date will be used.
 - If the imputed AE start date and is after date of death, then date of death will be used
 - If the imputed AE start date is in the same month and year but after the 1st subsequent therapy start date, then 1st subsequent therapy start date will be used.
- If the imputed date is for an AE end date and is after the death date, then the death date will be used, or if the imputed AE end date is before the AE start date, then the AE start date will be used.
- The AE imputation rule will be used for concomitant medication.

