6.1.1. All Adverse Events

The verbatim terms used in the CRF by investigators to identify AEs will be coded using the Medical Dictionary for Regulatory Activities (MedDRA), version 19.0 or higher. These coded AE terms are referred to as preferred terms (PT); classification into System Organ Class (SOC) is a result of the coding process.

Treatment-emergent AEs (TEAEs) are defined as 1) those that occur in TEAE period as defined below 2) present before first dose, but worsened in toxicity grade during treatment; 3) had missing start date and its end date is during the treatment; 4) was a drug-related event. Drug-related AEs are those assessed by investigator as being possible, probable, or very likely

related to study drug. To determine TEAE, partially missing AE start dates will be imputed according to the rules stated in Section [2.7](#).

For each TEAE, the percentage of subjects who experience at least 1 occurrence of the given event will be summarized. Tables will be sorted by frequency in incidence (the highest to lowest incidence).

For subjects using CYP3A inhibitor during treatment-emergent period, all TEAEs will be summarized by SOC, PT, maximum severity, any CYP3A inhibitor (Yes vs. No), and strong CYP3A inhibitor (Yes vs. No).

Treatment-Emergent Period

In general, the treatment-emergent period is defined as the time from first dose date through 30 days after last dose date, or day before subsequent antilymphoma therapy or a conditioning regimen for stem cell transplantation, whichever occurs first.

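### SAP 2.7 can place partially dated adverse event onsets outside the treatment-emergent period that SAP 6.1.1 defines, in one case by a single day

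*SAP*

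**What the plan says.** **The period.** SAP 6.1.1 opens the period at first dose and closes it 30 days after the final dose, unless another limit comes earlier. That limit is given as "day before subsequent antilymphoma therapy or a conditioning regimen for stem cell transplantation, whichever occurs first". The same section lets the imputed date decide the classification, by pointing to Section 2.7: "To determine TEAE, partially missing AE start dates will be imputed according to the rules stated in Section".

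**The defaults (SAP 2.7).** For a missing day: "If only day is missing but year and month are available, then the 15th of the month will be used". For a missing month and day: "If only year is present but month and day are missing, then June 30th will be used".

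**The adjustments to an imputed AE start (SAP 2.7), applied in order.**
1. Move to first dose, or to last dose + 30 days, but only when the imputed date lies in the same month and year as that limit.
2. Move back to a known AE end date if the imputed start is later.
3. Move back to the date of death if the imputed start is later.
4. When the imputed start falls later in the calendar month in which the first subsequent therapy begins, "then 1st subsequent therapy start date will be used".

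**What counts regardless of onset date (SAP 6.1.1).** Drug-related events count, as do events present before first dose that worsened in grade during treatment. An event with a missing start date counts if its end date is during treatment.

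**The protocol.** Protocol 11.7 takes treatment-emergent events up to 30 days after the last dose and has no cut at subsequent therapy.

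**The concern.** Two parts of the SAP do not fit together. Section 6.1.1 closes the period the day before subsequent therapy, while step 4 of Section 2.7 pulls a late imputed onset back to the therapy start, one day too late to count. The companion rule for last dose + 30 lands on the last day inside its limit, so step 4 looks like a drafting slip.

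It also goes against the likely truth. Under Protocol 12.3.1, collection of AEs not related to treatment stops when subsequent systemic antineoplastic therapy starts. An unrelated AE recorded in that month therefore most likely began before therapy.

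The year-only rule reaches the same result by another route, because 30 June has no connection with the subject's treatment dates and is almost never corrected.

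Treatment-emergent status feeds most of SAP Table 4: the serious, Grade 3 or worse, discontinuation, fatal and exposure-adjusted summaries. The planned control arm is 72 − 48 = 24 subjects, so one subject is 1/24, about 4 percentage points. The events exposed to loss are those the investigator did not call drug-related, and that judgement is made in an open-label trial.

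**Working it through.** The plan states no figure to reproduce. The check applies the date rules and compares each result with the period.

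**A. Day missing, event in the month subsequent therapy starts.** Let S be the day of the month on which therapy starts. The default onset is the 15th, and the period ends at the earlier of S − 1 and last dose + 30. No end date or death date intervenes. Illustration: first dose 1 July 2019, last dose 25 September 2019 (so last dose + 30 is 25 October), event in October 2019.

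| S | Imputed onset | Period ends | Result |
|---|---|---|---|
| 1 | 1 | last day of previous month | outside, correctly: no day of the month is inside |
| 2 to 14 | S | S − 1 | outside, though days 1 to S − 1 were inside |
| 15 | 15 (not after S, so not moved) | 14 | outside, though days 1 to 14 were inside |
| 16 to 31 | 15 | 15th or later | inside |

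For S = 10 October, the 15th is moved to the 10th while the period ended on the 9th. Fourteen start days (2 to 15) misplace the event. Two situations prevent this: a known AE end date before S (step 2), and a last dose + 30 earlier in that month than both S and the 15th (step 1).

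**B. Month and day missing.** Because 30 June is the last day of its month, it can never precede a first dose in June, so the first-dose correction never acts on it. The last dose + 30 correction acts only when that limit falls on 1 to 29 June, which is 29 start dates. Assume first doses spread evenly over 365 days, true onsets uniform over the period, no subsequent therapy and no informative end date. For a period of L = treatment days + 30, the share placed outside is about

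1 − (L + 29)/365.

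Treatment lengths come from the cycle rules in SAP 2.5 (3 × 21 = 63, 3 × 28 = 84) and the monotherapy in SAP 1.2 (84 + 3 × 28 = 168).

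| Treatment days | L | (L + 29)/365 | Outside |
|---|---|---|---|
| 63 | 93 | 122/365 = 33.4% | 66.6% |
| 84 | 114 | 143/365 = 39.2% | 60.8% |
| 168 | 198 | 227/365 = 62.2% | 37.8% |

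A day-by-day count gives 66.6%, 60.8% and 39.6%. The last differs slightly because a 198-day period can straddle 31 December, and onsets in the other calendar year receive that year's 30 June. For control subjects on 28-day cycles, the last scheduled chemoimmunotherapy is Day 9 of Cycle 3 (Protocol Tables 5 and 6). So L = 28 + 28 + 9 + 30 = 95, and 1 − 124/365 = 66.0%.

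Examples: first dose 2 September 2019 gives 30 June 2019, before treatment. Treatment from 7 January to 31 March 2019 (period ending 30 April) gives 30 June 2019, after the period. Neither is adjusted.

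**C. Day missing, no subsequent therapy.** No onset falls outside for any of the three durations. The first-dose and last dose + 30 corrections work as intended.

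**The case against.** The strongest reply is that little is really lost. Drug-related events and pre-dose events that worsened stay in whatever their date. A known end date rescues some events imputed too late. Protocol 12.3.1 requires the duration of each episode to be recorded, and Protocol 17.5 allows data queries, so year-only onsets should be rare. All of this stands, and it keeps the point small. It does not remove the one-day mismatch, which needs no assumption to show. The missing-start-date criterion does not clearly help: the SAP does not say that it covers partial dates, and it needs an end date during treatment.

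It can also be said that the exclusion at S comes from the SAP's period being narrower than the protocol's. That is right: under Protocol 11.7 day S could still count. But the SAP's period is the one that will be programmed.

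Four stronger readings are tempting and not supported:
- A reader might divide the period by 365 and infer that about three quarters of year-only onsets are lost (for L = 95, 1 − 95/365 = 74%). That omits the last dose + 30 correction; with it the figure is 66%, and it is lower for longer treatment.
- A reader might infer that every missing-day event is lost whenever subsequent therapy starts before the 15th. Step 2, step 1 and the retained categories all prevent this in some cases. With S on the 1st, exclusion is correct.
- A reader might infer that both rules always understate toxicity. The 30 June rule has no fixed direction. AEs are collected from consent, and a screening event can be drawn into the period as well.
- A reader might want every uncertain onset set to first dose. That is a preference of convention and would distort onset timing.

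**Conclusion.** The point holds as a minor but definite error in the SAP text. For subsequent therapy starting on days 2 to 15, Section 2.7 puts a missing-day onset on the first day after the Section 6.1.1 period. This affects events not judged drug-related that are ongoing or end on or after the therapy start, where no earlier last dose + 30 in that month has already placed the onset inside.

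For year-only onsets, about 67%, 61% and 40% of true treatment-emergent events are placed outside for 63, 84 and 168 treatment days. These shares are illustrative. They rest on uniform onsets, first doses spread over the year and no informative end date, and they apply before retained drug-related and worsened events are added back. Because they depend on treatment length, they need not be equal in the two arms. The documents do not give the number of partial dates, so the number of affected events cannot be stated; it is probably small.

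**What to change.** Two wording changes in SAP 2.7, with matching programming:

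1. **Subsequent therapy.** When the imputed AE start is in the same month as, and on or after, the first subsequent therapy start, use that start date minus 1 day, not earlier than first dose. The words on or after are needed for a start on the 15th. If therapy starts on the 1st, leave the event outside, since no day of the recorded month is in the period.
2. **Year-only AE onsets.** If the known year overlaps the treatment-emergent period, limit the imputed date to that overlap, unless the AE end date shows onset outside it.

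Applied to the cases above, the misplaced start days in A fall from 14 to 0, and the share outside in B falls to 0% for all three durations. The definition of conditioning in Section 6.1.1 should be used for the start date in both sections, so that the two refer to the same day.

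The cost is a few uncertain events counted as treatment-emergent that may not have been. Design, data collection and the efficacy analyses are unaffected.
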